#### 10.1 EXTENT OF EXPOSURE

The number of treatments received will be summarized by treatment group for the Safety Population.

#### 10.2 ADVERSE EVENTS

Adverse events will be coded by system organ class and preferred term using the *Medical Dictionary for Regulatory Activities*, version 25.1 or newer.

An AE will be considered as a treatment-emergent adverse event (TEAE) if the AE began or worsened (increased in severity or became serious) on or after the date of the first dose of double-blind study treatment.

A TEAE for treatment cycle 1 is an adverse event with onset after the initiation of study treatment or became serious after the initiation of study treatment for cycle 1.

In each of the analysis periods (treatment cycle 1 in the double-blind period, open-label period, BOTOX cycle, or BOTOX overall), a specific TEAE will only count once per participant, associated with its worst severity during the time period of interest. Unless stated otherwise, the methods of analyses described in this section will be applied to each of the study period.

TEAEs will be summarized for each treatment group by treatment cycle 1 in the double-blind period, open-label period, by BOTOX cycle, and BOTOX exposure overall. Participants will be counted according to the treatment received at baseline (Placebo or BOTOX 72 U) for treatment cycle 1. For open-label period and Any BOTOX exposure tables, participants will be summarized according to the treatment received at cycle 1 baseline and treatment received during open-label (Placebo/BOTOX 72 U or BOTOX 72 U/BOTOX 72 U and Total). The only

exception is BOTOX cycle 3, where participants will be summarized by BOTOX 72 U/BOTOX 72 U.

Overall summary of AEs will be provided on a per-participant basis for categories of TEAEs, treatment-related TEAEs, deaths, serious adverse events (SAEs), AEs leading to discontinuation, and possible distant spread of toxin (PDSOT).

The number and percentage of participants reporting TEAEs in each treatment group will be tabulated by system organ class (SOC) and preferred term, and further categorized by severity and causal relationship to the study treatment separately. If more than 1 AE is coded to the same preferred term for the same participant, the participant will be counted only once for that preferred term using the greatest severity and strictest causality for the summarization by severity and causal relationship.

The incidence of TEAEs will be summarized by preferred term and treatment.

An AE will be considered a treatment-emergent serious adverse event (TESAE) if it is a TEAE that additionally meets any SAE criterion.

The number and percentage of participants in the Safety Population who have TESAEs or TEAEs leading to premature discontinuation of the study treatment will be summarized by SOC, preferred term, and treatment.

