Period 1 (Days 1 through 180) will be a double-blind, randomized, placebo-controlled, single-treatment design, which will assess the safety and efficacy of BOTOX treatment of MMP. On Day 1, participants will be randomized in a 3:1 ratio to receive BOTOX 72 U or placebo. Randomization will be stratified at each investigator site by the participant's baseline MMPS Grade (4 or 5). On Day 180, final Period 1 assessments will be collected, after which all participants will continue into Period 2, the open-label treatment portion of the study.

Period 2 (Days 180 through 540) will be open-label. All BOTOX and placebo-treated participants from Period 1 are eligible to receive up to 2 open-label treatments of BOTOX 72 U in Period 2 if they meet protocol-specified retreatment criteria on or after the Day 180 visit. If the participant does not meet the retreatment criteria at the Day 180 visit, he or she will be reassessed at the next visit. For Treatment 2, participants who qualify can be retreated from the Day 180 visit through the Day 420 visit. For Treatment 3, the earliest visit that participants may qualify and receive the third treatment is the Day 270 visit (3 months after the earliest visit for Treatment 2 [Day 180 visit]). The last visit that participants may qualify and receive treatment

(either Treatment 2 or Treatment 3) is

Retreatment Criteria:

- Participant has presence of MMP of at least marked (Grade 4) on each side, as assessed by the investigator using the MMPS, AND
- Females of childbearing potential must have a negative pregnancy test prior to treatment,
 AND
- If it is the third treatment, at least 3 months have lapsed since the previous study treatment

If a participant qualifies for retreatment in Period 2 and declines it, retreatment will not be administered at that visit and the participant's reason for declining retreatment will be captured on the eCRF. If the participant still meets retreatment criteria at the next visit (up to Day 420), he or she may receive retreatment at that time.

Number of Participants:

Approximately 360 participants will be enrolled in order to have 306 participants complete the study based on an anticipated dropout rate of 15%.

- Approximately 235 participants will be enrolled from China (mainland).
- Approximately 75 participants will be enrolled from Canada.
- Approximately 50 participants will be enrolled from Taiwan.

Number of Sites:

Approximately 30 sites in China (mainland), Canada, and Taiwan

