9.4.2.1. Adverse Events

An AE will be considered a TEAE if:

- The AE began on or after the date of the first dose of study intervention; or
- The AE was present before the date of the first dose of study intervention, but increased
 in severity or became serious on or after the date of the first dose of study intervention

An AE will be considered a TESAE if it is a TEAE that additionally meets any SAE criteria.

The number and percentage of participants reporting TEAEs in each study intervention group will be tabulated by system organ class and preferred term and by system organ class, preferred term, and severity.

The number and percentage of participants reporting treatment-related TEAEs in each study intervention group will be tabulated by system organ class and preferred term.

BOTOX

If more than 1 AE is coded to the same preferred term for the same participant, the participant will be counted only once for that preferred term using the most severe and most related occurrence for the summarizations by severity and by relationship to study intervention.

Summary tables will be provided for participants with SAEs and participants with AEs leading to discontinuation if 5 or more participants reported such events. Listings of all AEs, SAEs, and AEs leading to discontinuation by participant will be presented.

The definitions of an AE and SAE can be found in Appendix 2.

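### The SAP's cycle-1 TEAE rule omits AEs that began before injection and then increased in severity, contrary to its own general rule and the protocol; the undercount is probably small and may be zero

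*SAP*

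**What the plan says.** SAP 10.2 opens with a general rule for calling an AE treatment-emergent: "if the AE began or worsened (increased in severity or became serious) on or after the date of the first dose of double-blind study". The reference point is thus the first double-blind injection. The next sentence sets a rule for cycle 1 alone: "A TEAE for treatment cycle 1 is an adverse event with onset after the initiation of study treatment or became serious after the initiation". Its reference point is the start of the cycle-1 injection. Both sentences are complete in the public text; nothing appears to be blacked out.

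Protocol 9.4.2.1 has two routes to a TEAE. The first is onset on or after the first-dose date. The second is for events already present by then, which must have changed in one of two ways, the relevant words being "in severity or became serious on or after the date of the first dose of study intervention".

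Two further statements in SAP 10.2 bear on which rule governs cycle 1 and who is compared there: "Unless stated otherwise, the methods of analyses described in this section will be applied to each of the study period", and "Participants will be counted according to the treatment received at baseline (Placebo or BOTOX 72 U) for treatment cycle 1". The protocol synopsis adds: "Period 2 (Days 180 through 540) will be open-label".

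**The concern.** The general SAP rule and the protocol recognise three triggers: onset, increase in severity, and becoming serious. The cycle-1 sentence names only onset and becoming serious. A programmer would follow the cycle-1 sentence for the cycle-1 tables, because the general methods carry over only where nothing else is stated, and here something else is stated.

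Cycle 1 is where placebo is compared with BOTOX; every later injection is open-label BOTOX. The narrower rule therefore sits on the one AE table with a control arm, and AE incidence compared with placebo is part of the primary safety objective (vital signs are the other part and are not affected). The AESI and distant-spread tables in SAP 10.3 and 10.4 are also built on TEAEs, so any cycle-1 version of them would inherit the rule.

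**Working it through.** The plan states no figure for this point, so there is none to reproduce. The check compares the definitions by class of event and then gives a scale.

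**Step 1. Which events each rule counts**

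| Event | General SAP rule | Cycle-1 rule |
|---|---|---|
| Starts after injection | counted | counted |
| Starts after injection, then worsens | counted | counted, at worst severity |
| Starts before injection, later becomes serious | counted | counted |
| Starts before injection, increases in severity only | counted | **not counted** |
| Starts on Day 1 before the injection | counted (date rule) | **not counted** |
| Starts before Day 1, unchanged | not counted | not counted |

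The protocol rule gives the same result as the general SAP rule in every row. The cycle-1 set lies wholly inside the general set, so the cycle-1 rule can lose events but cannot add any.

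**Step 2. Whether the lost class can occur**

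AEs are collected from consent, and those starting before dosing are recorded as pretreatment AEs (protocol 8.3.1). Later information on an AE goes into the eCRF entry already made for it (protocol 8.3.3). A pretreatment AE that worsens can therefore keep its pre-injection start date, and that is the record the cycle-1 rule drops.

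**Step 3. Timing**

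The general rule works by date and includes the first-dose date. The cycle-1 rule works from the start of treatment. AEs are collected both before and after injection at treatment visits (SAP Table 1, note m), so a Day 1 event before injection is classified differently by the two rules. SAP 17.11 also sets some incomplete or missing start dates to the first-dose date. Such an event meets the date rule, but without a clock time its status under the cycle-1 rule is unclear.

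**Step 4. Scale**

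Inputs: 360 planned participants, 270 BOTOX and 90 placebo (SAP 15.0). Let q be the proportion with a pre-injection AE that increases in severity afterwards without becoming serious and stays on one record. The documents give no value, so q from 0% to 3% is an assumption. The expected number affected is n × q, and the chance of at least one among 360 is 1 − (1 − q)^360.

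| q | BOTOX (270q) | Placebo (90q) | Total (360q) | Chance of at least one |
|---|---|---|---|---|
| 0% | 0 | 0 | 0 | 0 |
| 0.5% | 1.35 | 0.45 | 1.8 | 0.835 |
| 1% | 2.7 | 0.9 | 3.6 | 0.973 |
| 2% | 5.4 | 1.8 | 7.2 | 0.999 |
| 3% | 8.1 | 2.7 | 10.8 | above 0.999 |

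These are participants affected, not participants lost from the any-TEAE row. Someone with another cycle-1 TEAE stays in that row and loses only a preferred-term entry.

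**Step 5. Effect on the treatment difference**

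If proportions q_B (BOTOX) and q_P (placebo) lose their count in a given row, the difference in that row shifts by q_B − q_P. With equal proportions the shift is zero. The documents give no basis for choosing unequal ones.

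**The case against.** The strongest reply is that the lost class is narrow. Protocol Appendix 2 treats the exacerbation of a chronic or intermittent condition, including greater intensity, as an AE in its own right. Worsening of a long-standing headache would then normally be entered as a new AE with a post-injection start, and counted. What remains is mainly AEs arising between consent and injection, and screening runs only from Day -14 to Day -1. Participants must be healthy, and those with known or suspected TMJD are excluded, so aggravated jaw complaints are a poor example. The Phase 2 treatment-related events specific to the injection (mastication disorder, facial paresis, injection site pain) and the AESIs would be expected as new events after injection. Listings of all AEs are planned, so no event is hidden.

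All of this stands as a limit on size. It does not remove the conflict. The exacerbation text concerns chronic or intermittent conditions, while an AE already reported during screening can be updated on its existing record. No other section restores the severity trigger for cycle 1.

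On timing, the cycle-1 wording fits the notion of a pretreatment AE in protocol 8.3.1 better than the date rule does. That is fair: the mismatch has to be settled, and it does not by itself show that the cycle-1 sentence is the wrong one.

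**Conclusion.** The cycle-1 sentence conflicts with the general SAP definition and with protocol 9.4.2.1, and it can only undercount. The events lost are AEs that began before the Day 1 injection, stayed on one record, and increased in severity without becoming serious. Day 1 events before injection are also classified differently. The size cannot be computed from the documents. At an assumed 0% to 3% it is 0 to about 11 of 360 participants, and it is probably at the low end.

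A reader might infer three stronger things that the documents do not support:

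- *All worsening after injection is missed.* It is not: events that start after injection are counted at their worst severity.
- *The comparison with placebo is biased.* The rule is the same in both arms, so bias needs unequal worsening rates, for which there is no evidence here.
- *The cycle-1 table will fail to reconcile with an overall table.* SAP 10.2 names cycle 1, the open-label period, BOTOX cycles and overall BOTOX exposure, with no all-study TEAE table that includes placebo exposure. Cycle 1 and overall BOTOX exposure differ by design for participants who started on placebo.

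The point is worth correcting because the inconsistency is certain, it falls on the controlled AE table, and the remedy is cheap.

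**What to change.** Replace the cycle-1 sentence in SAP 10.2 with, for example: *An AE is treatment-emergent for treatment cycle 1 if its onset, an increase in its severity, or its becoming serious falls on or after the cycle 1 treatment date and before the date of the next study treatment (or by study exit if there is none).* This agrees with protocol 9.4.2.1 and with the cycle boundaries in SAP 17.2. Use the same three triggers for every cycle, each with its own treatment date.

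The date rule also settles Day 1 events and start dates imputed to the first-dose date: they count. The protocol's date rule already counts them. If the sponsor prefers to leave out Day 1 events before injection, protocol 9.4.2.1 and the general SAP rule would have to change too, and clock times would be needed.

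The cost is one sentence and one derived flag, plus a slightly higher reported TEAE incidence, including any Day 1 pre-injection events. The change should be made before database lock and unblinding.

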## Missing month and day

- If the year of the incomplete start date is the same as the year of the first dose of study treatment, the month and day of the first dose of study treatment will be assigned to the missing fields
- If the year of the incomplete start date is before the year of the first dose of study treatment, December 31 will be assigned to the missing fields
- If the year of the incomplete start date is after the year of the first dose of study treatment,
   January 1 will be assigned to the missing fields

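### The SAP's cycle 1 TEAE definition leaves out worsening in severity, so some protocol-defined TEAEs are missing from the only AE summary with a concurrent placebo group

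*SAP*

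**What the plan says.** Protocol Section 9.4.2.1 gives a TEAE two routes. The first is onset: "The AE began on or after the date of the first dose of study intervention; or". The second covers an event that was already there: "The AE was present before the date of the first dose of study intervention, but increased", continuing "in severity or became serious on or after the date of the first dose of study intervention".

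The general rule in SAP Section 10.2 has the same content. An AE is treatment-emergent "if the AE began or worsened (increased in severity or became serious) on or after the date of the first dose of double-blind study treatment".

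The SAP then adds a separate definition for the first cycle: "A TEAE for treatment cycle 1 is an adverse event with onset after the initiation of study treatment or became serious after the initiation" of treatment in that cycle. It has two limbs, onset and becoming serious. Section 10.2 also says how the cycle 1 tables are laid out: "Participants will be counted according to the treatment received at baseline (Placebo or BOTOX 72 U) for treatment cycle 1".

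For partial AE start dates, SAP Section 17.11 imputes to the dosing date in several cases. For example, when month and day are missing and the year is the dosing year, "the month and day of the first dose of study treatment will be assigned to the missing fields".

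**The concern.** The cycle 1 definition differs from the protocol and from the SAP's general rule in two ways, and the SAP gives no reason for either.

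- **Severity.** It has no limb for an increase in severity, although it keeps the limb for becoming serious.
- **Cut-off.** It replaces a cut-off that takes in the whole dosing date with one that begins once treatment has been initiated.

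Incidence of AEs against placebo is the endpoint of a primary objective (SAP Section 5.1). In the open-label, BOTOX-cycle and BOTOX-overall summaries everyone has received BOTOX, so only cycle 1 offers a concurrent placebo group. Relative to the protocol, the narrower sentence can only remove events from that comparison. AESIs and possible distant spread events are themselves defined as TEAEs (SAP Sections 10.3 and 10.4), so the narrower rule could carry into their cycle 1 tables. Nothing says which definition prevails, and two programmers could each follow the text and obtain different cycle 1 counts.

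**Working it through.** There is no figure in the plan to reproduce, because the question is one of definition. The check applies each rule to the same six test events.

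**Inputs**

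- TEAE rules: Protocol Section 9.4.2.1; SAP Section 10.2 (general and cycle 1).
- AEs arising between consent and dosing are recorded in the eCRF as pretreatment AEs: Protocol Section 8.3.1.
- Later information on an AE goes into its existing eCRF entry, which suggests that a worsened event keeps its pre-dose onset date: Protocol Section 8.3.3.
- Imputation of partial start dates: SAP Section 17.11.
- Group sizes of 270 BOTOX and 90 placebo: SAP Section 15.0.

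**Classification.** The cycle 1 sentence is read in two ways: by clock time relative to the injection, and by a strict comparison of calendar dates.

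| Test AE | Protocol and SAP general rule | Cycle 1 rule, clock time | Cycle 1 rule, strict date |
|---|---|---|---|
| 1. Onset Day -5, mild to moderate on Day 10, not serious | counted | left out | left out |
| 2. Onset Day -5, serious on Day 10 | counted | counted | counted |
| 3. Onset Day 1, before injection | counted | left out | left out |
| 4. Onset Day 1, after injection | counted | counted | left out |
| 5. Start date imputed to the dosing date, no time | counted | undetermined | left out |
| 6. Onset Day 30 | counted | counted | counted |

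Row 1 is the firm result: the event is lost however *after* is read, provided it stays under its original onset date. Row 3 is also lost under both readings. Row 5 depends on the reading. Row 4 is lost only under the strict date reading, which the documents do not call for.

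**Scale**

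- One omitted participant lowers the rate of that event by 1/270 = 0.37 percentage points on BOTOX and 1/90 = 1.11 points on placebo.
- The documents give no rate of pretreatment AEs that later worsen. Purely as an assumption, take 0.2% to 2% of participants:
  - BOTOX: 270 × 0.002 = 0.54, to 270 × 0.02 = 5.4.
  - Placebo: 90 × 0.002 = 0.18, to 90 × 0.02 = 1.8.

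**The case against.** The best defence is that the sentence only assigns events to a cycle and that the general rule just before it still decides what counts as a TEAE. That is possible, but the SAP does not say so, and the sentence is worded as a definition.

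The defence also has good grounds for calling the gap narrow. Protocol Appendix 2 treats an exacerbation of a chronic or intermittent pre-existing condition, including greater intensity, as an AE in its own right; recorded that way, it has a post-dose onset and is kept. Only AEs that start between consent and dosing are exposed, screening runs from Day -14 to Day -1, and participants must be healthy. Events that become serious are retained, and the protocol plans listings of all AEs. All of this limits the size. None of it supplies the missing limb.

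A reader might infer more than the documents support:

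- **That injection-day events in general are lost.** Read naturally, the sentence keeps events that start after the injection on Day 1. SAP Table 1 (footnote m) requires AEs to be collected both before and after study treatment at each treatment visit, and Section 17.2 starts a cycle on the day of treatment. No section prescribes a strict date comparison.
- **That about nine BOTOX participants with injection site pain would vanish.** Applying the Phase 2 rate gives 5/150 × 270 = 9. That rate comes from a 12-month study at 24 to 96 U in which some participants were treated twice, and no onset day is given. The nine would be lost only if all began on Day 1 and a strict date comparison were used.
- **That a worsened event appears in no cycle table.** The narrow sentence covers treatment cycle 1 only. No comparable restriction is visible for the BOTOX-cycle or BOTOX-overall summaries, so a BOTOX-arm event might be counted there.

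**Conclusion.** The inconsistency is real and should be corrected before programming and unblinding. The severity omission is the main point. As written, the cycle 1 table excludes some events that the protocol and the SAP's general rule call treatment-emergent. The cut-off wording is secondary: it excludes Day 1 events before the injection and leaves events imputed to the dosing date without a clear status.

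The effect is probably small. Its size cannot be obtained from the documents, and the range in the working rests on an assumed rate. The main point also assumes that a worsened pretreatment AE stays under its first onset date, which Protocol Section 8.3.3 suggests but does not settle.

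A reader might infer that the rule favours BOTOX. The documents do not show this: the same rule applies to both arms, and nothing indicates in which arm more events would be lost. Nor is cycle 1 strictly a randomized comparison. The Safety Population is analysed by treatment received (SAP Section 6.2), and data after Day 180 but before retreatment are ascribed to cycle 1 treatment (SAP Section 10.0). It is accurate to call it the only AE summary with a concurrent placebo group.

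**What to change.** Replace the cycle 1 sentence in SAP Section 10.2 with:

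*A TEAE for treatment cycle 1 is an AE that began, increased in severity, or became serious on or after the date of the double-blind injection and no later than the last day of cycle 1 (Section 17.2).*

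This restores the severity limb and uses the same date-based cut-off as Protocol Section 9.4.2.1 and the SAP's general rule. All six test events are then classified as the protocol classifies them, and a start date imputed to the dosing date counts without further argument. Do not add a clock-time qualifier here. Both governing rules use the date alone, and a qualifier would again exclude Day 1 events known to precede the injection.

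The cost is one SAP sentence and one condition in the AE derivation. Sample size, power and alpha do not change. Cycle 1 TEAE counts may rise slightly in both arms.

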Danied 2 (Davis 190 through 540/Study Evit)

Period 2 (Days 180 through 540/Study Exit)

Day 180 is considered both the end of Period 1 and the beginning of Period 2. After Period 1 assessments are collected, the participant will enter Period 2 and will be assessed for retreatment. If the participant does not meet the retreatment criteria at Day 180, he or she will be reassessed at the next visit. All BOTOX and placebo-treated participants from Period 1 are eligible to receive up to 2 open-label treatments of BOTOX 72 U in Period 2 *if* they meet the following retreatment criteria (also see Section 6.6) on or after the Day 180 visit.

- Participant has bilateral marked (Grade 4) or very marked (Grade 5) MMP, as assessed by the investigator using the MMPS, AND
- Females of childbearing potential must have a negative pregnancy test prior to treatment,
 AND
- If it is the third treatment, at least 3 months have lapsed since the previous study treatment (no retreatment earlier than 84 days)

During Period 2, participants will attend all follow-up visits (Days 210, 240, 270, 300, 330, 360, 390, 420, 450, 480, 510, and 540). For Treatment 2, participants who qualify can be retreated from the Day 180 visit through the Day 420 visit. For Treatment 3, the earliest visit that participants may qualify and receive the third treatment is Day 270 (3 months after the earliest visit for Treatment 2 [Day 180]). The last day that a participant can receive either Treatment 2 or 3 is Day 420; this ensures a 120-day safety and efficacy follow-up period by Day 540/study exit. A participant who meets retreatment criteria may decline retreatment if they choose, and their reason will be captured on the eCRF. If the participant still meets retreatment criteria at the next visit (up to Day 420), he or she may receive retreatment at that time.

In Period 2, participants will receive up to 2 additional treatments. Based on individual variability in time to meet retreatment criteria noted in the Phase 2 Study 191622-130, retreatment timepoints are not expected to be synchronized among the participants in the study.

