## 5.2 CLINICAL HYPOTHESES

BOTOX treatment of MMP is more effective than placebo as measured by investigator assessment of MMP severity using the MMPS.

BOTOX has an acceptable safety profile after single and repeat MMP treatment.

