#### 17.2 TREATMENT CYCLES

A treatment cycle is considered to start on the day of treatment with study medication and end on the day prior to the next study treatment or on the study exit day if there are no subsequent treatments.

[figure not shown]

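### By-BOTOX-cycle TEAE percentages are crude although cycle lengths differ, so background and late-onset events can differ between exposures with no change in risk

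*SAP*

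**What the plan says.** SAP 10.2 sets out the adverse event tables: "TEAEs will be summarized for each treatment group by treatment cycle 1 in the double-blind period, open-label period, by BOTOX cycle", and for BOTOX exposure overall. The statistic is the number and percentage of participants, with a given TEAE counted once per participant in each analysis period. Only participants who receive BOTOX in both periods can appear in BOTOX cycle 3. Placebo starters therefore enter BOTOX cycle 1 with their first open-label injection.

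SAP 17.2 has a cycle begin on the day of treatment and "end on the day prior to the next study treatment or on the study exit day if there are no subsequent treatments". SAP 10.0 assigns safety data after Day 180 but before any retreatment to cycle 1.

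Protocol 4.1 sets the timing:

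- A participant who meets the criteria may have the second treatment at any visit between Days 180 and 420.
- On the third treatment it says: "For Treatment 3, the earliest visit that participants may qualify and receive the third treatment is Day 270", with "no retreatment earlier than 84 days".
- "The last day that a participant can receive either Treatment 2 or 3 is Day 420", which leaves 120 days to study exit at Day 540.

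On exposure, SAP 10.1 says: "The number of treatments received will be summarized by treatment group for the Safety Population". The visible text of SAP 10.1 and 10.2 has no follow-up time, person-time rate or common post-injection window. SAP 5.2 gives as a clinical hypothesis that "BOTOX has an acceptable safety profile after single and repeat MMP treatment".

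**The concern.** A crude percentage depends on how long participants are observed as well as on risk. Here the observation time differs between cycles, and between participants within a cycle, because the next injection ends the cycle. Protocol 4.1 itself does not expect retreatment times to be synchronised.

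Period 2 has no concurrent control. A reader asking whether repeat treatment is as well tolerated as the first will naturally look across the by-cycle columns. For events that accrue steadily, such as the background infections seen in Phase 2, those columns can differ only because one cycle was longer. A difference could be read as a safety trend that does not exist, or a real change in late or background events could be masked.

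**Working it through.** **The plan's own figure.** Protocol 4.1 gives 120 days of follow-up after the last permitted treatment: 540 - 420 = 120. This reproduces.

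**Cycle lengths.** These use the nominal visit days, with first and last day counted as in SAP 17.2, and assume completion.

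- Cycle 1 is shortest with retreatment at Day 180 (Days 1 to 179, 179 days) and longest with no retreatment (540 days).
- Cycle 2 is shortest at the stated 84-day minimum (270 - 180 = 90 on nominal visits) and longest at 540 - 180 + 1 = 361 days.
- Cycle 3 is shortest at 540 - 420 + 1 = 121 days and longest at 540 - 270 + 1 = 271 days.

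Rounded, these are about 180-540, 84-360 and 120-270 days for participants on BOTOX throughout. For placebo starters, BOTOX cycle 1 is the second treatment cycle (about 84-360 days) and BOTOX cycle 2 is the third (about 120-270 days). A pooled BOTOX cycle 1 column therefore mixes lengths from about 84 to 540 days.

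**Effect on a background event.** Protocol 4.2 gives nasopharyngitis in 8.0% of BOTOX-treated Phase 2 participants, and Protocol 2.1 gives that study as 12 months. Assume that 8.0% accrues at a constant hazard over 360 days:

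- λ = -ln(1 - 0.08)/360 = 0.0002316 per day
- expected percentage over d days = 1 - exp(-λd)

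| Days | 84 | 120 | 180 | 270 | 360 | 540 |
|---|---|---|---|---|---|---|
| Expected % | 1.9 | 2.7 | 4.1 | 6.1 | 8.0 | 11.8 |

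The extremes differ sixfold (11.8/1.9 = 6.2) with no change in risk.

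**Direction.** The same hazard along three permitted paths gives:

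| Treatments 2 and 3 | Cycle lengths (days) | Cycles 1/2/3 (%) |
|---|---|---|
| Days 180 and 270 | 179/90/271 | 4.1/2.1/6.1 |
| Days 270 and 420 | 269/150/121 | 6.0/3.4/2.8 |
| Days 180 and 360 | 179/180/181 | 4.1/4.1/4.1 |

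**Cohort level.** This simulation assumes lognormal time to relapse with log-SD 0.4, any-TEAE background of 40% per 360 days, no effect of repeat dosing and no dropout. None of these values is in the documents.

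- With a relapse median of 180-270 days, all participants in each cycle show 27-35% in cycle 1, 26-29% in cycle 2 and 19-22% in cycle 3.
- The share who reach cycle 3 falls from 57% at a median of 180 days to 12% at 270. Among those participants alone, cycle 1 shows about 24-25% against 19-22% in cycle 3, a gap of about 2.5 to 6 points.
- With a relapse median of 120 days the pattern is about 23.5%, 19% and 26%, so cycle 3 is the highest.

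**Early reactions.** If onset after injection is exponential with mean m days (assumed), the share captured by Day 84 is 1 - exp(-84/m). This is 99.75% for m = 14 and 94% for m = 30. By Day 120 it is 98% for m = 30.

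**The case against.** The case against is substantial, and most of it stands as a limit on the point.

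- **The events most relevant to the toxin are hardly affected.** Protocol 2.3 places adverse reactions generally in the first days to weeks. Every cycle of a completer is long enough to capture nearly all of these. SAP 10.2 also tabulates by causal relationship, and SAP 10.3 and 10.4 tabulate distant-spread events and events of special interest separately.
- **The tables are descriptive.** The hypothesis concerns an acceptable safety profile. No contrast between cycles is planned, and open-label and overall-BOTOX tables also bear on repeat treatment.
- **There is no fixed direction.** A reader might infer that incidence must change across cycles by construction. The documents do not support that: some permitted paths give equal cycles, and others give rises or falls.
- **Part of any gap is selection.** The fall from 27-35% to 19-22% compares everyone in cycle 1 with the earlier relapsers who reach cycle 3. In the same people it is much smaller.
- **Not everything is visible.** SAP 4.0 puts table specifications in a separate document, and parts of the SAP are missing from the public copy. An adjustment there cannot be excluded.

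These arguments do not remove the core. The by-cycle tables cover all TEAEs, including background and late ones, and the visible exposure summary gives a reader nothing with which to allow for unequal time at risk.

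**Conclusion.** The point holds as a limit on interpretation that is cheap to remove. Crude percentages by BOTOX cycle rest on observation times that vary from about 84 to 540 days, and no visible summary reports those times. For background and late-onset events the percentages can differ between first, second and third exposure with no change in risk, and the direction depends on when participants are retreated. The sixfold range (1.9% to 11.8%) compares the shortest and longest possible cycles and rests on an assumed constant hazard of 8% per 360 days. Cohort averages differ far less: about 2.5 to 6 points within the same participants, under the assumed 40% background and relapse medians of 180-270 days.

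A reader might go further and infer that a true rise in toxin reactions in cycle 3 would be hidden, or that the BOTOX-versus-placebo comparison is compromised. Neither follows. Early reactions are nearly all captured in the shortest cycle, and the point concerns successive BOTOX exposures, not the randomised comparison. No planned test is invalid. The data could also be adjusted later, since the dates are collected; the visible plan simply does not say that they will be.

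**What to change.** - **SAP 10.1:** add days of follow-up per BOTOX cycle, by treatment sequence.
- **SAP 10.2:** keep the full-cycle tables. Add, by treatment sequence, exposure-adjusted incidence per cycle (participants with the event per person-time at risk).
- **SAP 10.2:** add a supportive table of TEAEs with onset in a common window after each injection. The window should be no longer than the shortest interval the protocol allows between open-label injections, which it states as 84 days.
- **Selection:** show cycles 1 and 2 also for the participants who reach cycle 3, because neither adjustment removes selection of earlier relapsers.

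The cost is SAP wording and a few extra tables from dates already collected, with no change to trial conduct. Late-onset events drop out of the common-window table but remain in the full-cycle tables. Making the common-window table the main one would be a matter of preference; a supportive role is enough.
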